4.3.3 Open-Label Extension Treatment

Participants entering the OLE Treatment Period will undergo a 7-day dose titration (OLE Days 1 to 8) to receive open-label VTX002 60 mg following the same titration schedule for the VTX002 60 mg as shown in Table 2. Although dose titration would not be needed for participants who received VTX002 60 mg during the Induction Period/LTE Period, all participants entering the OLE Treatment Period will go through a full dose titration regimen to maintain the blind of the Induction Period/LTE treatment assignments.

5. PLANNED ANALYSES

Each planned analysis identified in this SAP will be performed after

- SAP is authorized by the study sponsor
- Database lock is completed as appropriate for the given planned analysis
- Study treatment is unblinded (if necessary) as appropriate for the given planned analysis

Any post hoc exploratory analyses completed to support planned study analyses not identified in this SAP will be documented and reported in the Clinical Study Report (CSR). Any results from these unplanned analyses will be clearly identified in the text of the CSR.

5.1 Interim Analyses

An interim database lock (iDBL), treatment unblinding, and data analysis will be conducted after all randomized participants have either completed the Induction Treatment Period or are no longer participating in the Induction Treatment Period for one of the following reasons:

- Participant enters OLE
- Participant enters LTE
- Participant withdraws from study

This interim analysis will be referred to as the Induction Period Analysis. The following rules will be used to determine which participant records are included in the Induction Period Analysis:

- For study participants entering one of the extension periods (either LTE or OLE), the Induction Period Analysis will be limited to data on or before the later of [a] the last available date of study drug administration during the Induction Treatment Period, and [b] latest visit date as reported in EDC, up to and including Visit 7 Week 13; and in cases where Visit 8/Week 13 occurs on the same day as Visit 7 Week 13, pre-dose Visit 8 data shall also be included. For concomitant medications and adverse events the start date will determine inclusion in Induction Period Analysis (or exclusion).
- For study participants not entering an extension period, all data is included

The focus of the Induction Period Analysis will be on data associated with the Induction Treatment Period – no OLE or LTE data will be incorporated into the Induction Period Analysis other than participant disposition information related to participant flow between study periods. The Induction Period Analysis will be limited to eCRF pages associated with the Induction Treatment Period as well as external vendor data (such as central laboratory data) associated with the Induction Treatment Period.

All data for the 13-week double-blind Induction Treatment Period will be analyzed. The primary and key secondary endpoints are measured and assessed at Induction Week 13, so this analysis will be considered final for the primary and key secondary endpoints. Outputs related to the Induction Treatment Period will be clearly labeled as such. The locked data used in support of the Induction Period Analysis will be treated as final and not subject to further data alterations. The SDTM and ADaM datasets derived from the locked data and used to support Tables, Listings, and Figures will be incorporated into a final Induction Treatment Period data package.

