17. SAFETY

17.1 Adverse Events

17.1.1 General Considerations

Adverse events are collected from the date and time of signing ICF and will be coded according to the MedDRA version 26.0 or higher. Adverse events with an onset prior to first dose of study treatment are collected as part of medical history. Adverse events with an onset on or after first dose of study treatment are collected on adverse event eCRFs. All AE tables will be summarized according to the actual treatment group with an appropriate safety set.

A treatment-emergent adverse event (TEAE) is either an AE occurring on or after the date and time of first study treatment intake, or an ongoing AE worsening in severity after the date and time of the first study treatment. If an AE date coincides with the date of first dose of study treatment and either the AE onset time or drug administration time is missing then the AE will be considered treatment-emergent. AEs having both start and end dates missing will also be considered treatment-emergent. AEs with a missing onset date and non-missing end date will be considered as TEAE unless end date is prior to the first drug administration. Adverse events with missing seriousness will be considered serious. Adverse events with missing severity will be considered to have CTCAE grade 3. Adverse events with missing relatedness will be considered related.

AEs with an onset prior to the date and time of first study treatment intake (i.e., during Screening) will be listed but will not be summarized unless they either result in a TEAE due to AE worsening in severity or are serious. TEAE summaries will be separately prepared for study periods of Induction Treatment Period, LTE, OLE, and for the entire study:

- TEAEs with an onset on or after date and time of first study treatment intake during the Induction Treatment Period but prior to last participation in the Induction Treatment Period will be associated with Induction. Also, TEAEs resulting from worsening of severity during Induction in an AE having onset during Screening will be associated with Induction. Summaries for the Induction Treatment Period will use the Safety Set. This set of TEAEs will be associated with the Induction Period Analysis.

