- TEAEs with an onset on or after the date and time of first study treatment intake during the LTE but prior to last participation in LTE will be associated with LTE. Also, TEAEs resulting from worsening of severity during LTE in an AE having onset prior to LTE will be associated with LTE. Summaries for the LTE will use the Safety-ET Set.
- TEAEs with an onset on or after the date and time of first study treatment intake during OLE but prior to last participation in OLE will be associated with OLE. Also, TEAEs resulting from worsening of severity during OLE in an AE having onset prior to OLE will be associated with OLE. Summaries for the LTE will use the Safety-ET Set.
- TEAEs with an onset on or after the date and time of first study treatment intake will be used for entire-study AE summarization. Note that a TEAE may also be an AE having onset during Screening for this purpose, but having worsening severity at some point after first study treatment intake. An AE considered as TEAE because of worsening severity will only be counted once, at maximum severity, for this purpose. Summaries for the entire study will use the Safety-ET Set.

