17.1.2 TEAE Summaries

An overall TEAE summary table will be presented separately for each of the study periods described in [Section 17.1.1](#). It will include the number and percentage of participants with at least one event of specified category. The following categories will be displayed:

- TEAE
- Treatment-emergent serious AE (SAE)
- Non-serious TEAEs
- TEAE/treatment-emergent SAE related to study treatment
- AE/TEAE leading to death.
- TEAEs Grade 4 or higher
- TEAEs Grade 3 or higher

- TEAEs Grade 2 or higher
- TEAEs leading to study treatment discontinuation
- TEAEs leading to study treatment interruption
- TEAEs by maximum CTCAE severity
- Related TEAEs by maximum CTCAE severity

The incidence of treatment-emergent SAEs, TEAEs, and non-serious TEAEs will be summarized separately, by the following, for each of the study periods described in [Section 17.1.1](#):

- SOC and PT, ordered by descending frequency of PT in VTX002 60 mg group
- SOC, PT, and relatedness to study treatment, ordered by decreasing frequency in VTX002 60 mg group
- SOC, PT, and maximum Common Terminology Criteria for Adverse Events (CTCAE) toxicity grade and ordered by decreasing frequency in VTX002 60 mg group.
- PT, ordered by descending frequency of PT in VTX002 60 mg group

Additionally, the incidence of treatment-related TEAEs, treatment-related SAEs, treatment-related non-serious TEAEs, TEAEs leading to study treatment interruption, TEAEs leading to premature discontinuation of study treatment, and TEAEs leading to death will be summarized separately, by SOC and PT, for each of the four types of TEAE summaries described in [Section 17.1.1](#) and ordered by descending frequency of PT in VTX002 60 mg group.

In summaries associated with a specific study period – either Induction, LTE, or OLE – if the same TEAE is reported for the same participant more than once, the TEAE is counted only once for each SOC by PT combination. In these study period tabulations, study treatment shall be considered to be the treatment a study participant actually receives during a given study period. If a study participant receives multiple study treatments during a given study period, adverse events for that participant will be tabulated according to the highest dose of study treatment received.

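### When the first open-label dose falls on the Visit 7 date, the date-only adverse-event sentence in SAP 5.1 conflicts with SAP 17.1.1 and with the rest of SAP 5.1

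*SAP*

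**What the plan says.** SAP 5.1 sets the cut for participants who enter the long-term extension (LTE) or the OLE. It keeps data through the later of the last Induction dosing date and the "latest visit date as reported in EDC, up to and including Visit 7 Week 13". Where Visit 8 shares a day with Visit 7, "pre-dose Visit 8 data shall also be included". For adverse events (AEs) and medications the rule is: "For concomitant medications and adverse events the start date will determine inclusion in Induction Period Analysis (or exclusion". The next paragraph keeps LTE and OLE data out, apart from disposition, and limits the analysis to Induction eCRF pages. It adds: "The locked data used in support of the Induction Period Analysis will be treated as final and not subject to further data alterations".

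SAP 17.1.1 assigns treatment-emergent AEs to periods. Events with onset from the first dose but "prior to last participation in the Induction Treatment Period will be associated with Induction", and that set is expressly tied to the Induction Period Analysis. The OLE set takes "TEAEs with an onset on or after the date and time of first study treatment intake during OLE". The rule for missing times begins "If an AE date coincides with the date of first dose of study treatment" and mentions no later dose. In the period tables of SAP 17.1.2, "study treatment shall be considered to be the treatment a study participant actually receives during a given study period".

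Protocol Table 3 footnote a provides for OLE Visit 1 on the day of the Week 13 visit. It allows a later day, within 3 days, only when a shared day is not possible. The OLE Day 1 dose is 3 mg (Protocol 6.3.1 with Table 8), followed by 6 hours of monitoring in clinic.

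**The concern.** One rule works by date and the other by date and time, and the usual rollover puts both periods on one date. For a former-placebo participant that date carries the first VTX002 dose ever taken. Protocol 2.2.2.5 reports that after a single dose the largest fall in heart rate came between 1 and 2 hours, with recovery by the interval starting at 3 hours. A first-dose cardiac event would therefore begin on the shared date. Bradycardia and AV conduction delay are targeted medical events in SAP 17.1.3.

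Followed literally, the SAP 5.1 sentence would enter such an event in the placebo column of the Induction tables. Former-active participants have already been exposed, so any misplacement would mainly raise the placebo count and narrow the drug-placebo difference. It would also sit in a data package that the SAP treats as final.

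**Working it through.** The plan gives no figure to reproduce, so the check applies each rule to one case. Let D be a date shared by Visit 7 and OLE Visit 1.

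- **AE on D, before the open-label dose.** SAP 5.1 includes it, and SAP 17.1.1 does not assign it to the OLE. There is no conflict, unless last participation in 17.1.1 is taken to mean the Visit 7 date. In that case the event precedes the OLE yet is not prior to the end of Induction, and it belongs to neither period.
- **AE on D, after the open-label dose.** The start-date sentence in SAP 5.1 includes it. The bar on OLE data in the same section excludes it. SAP 17.1.1 assigns it to the OLE.
- **AE on D, no onset time.** SAP 5.1 includes it. SAP 17.1.1 cannot place it, because the missing-time rule addresses only the first dose of study treatment and settles only whether the event is treatment-emergent. SAP 15.1.1 takes the first OLE dose from a start-date field.
- **AE after D.** It falls outside the cut and belongs to the OLE. The rules agree.

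The clear mismatch is therefore confined to events on D that start after the dose or have no recorded time.

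Other text does not settle it. The pre-dose limit names Visit 8, which is the LTE visit in the current protocol. SAP Table 10 maps it to the first OLE visit only for Protocol v1. For LTE entrants the treatment does not change, so only the period label is at stake. The eCRF-page limit helps only if AE pages are split by period. SAP 17.1.1 describes AE eCRFs without such a split, and the eCRF itself is not in the documents.

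On size, events moved = n × r. Here n is the number of placebo participants who roll over on the same day, and r is the chance of a cardiac AE starting on the day of the first 3 mg dose. The documents give neither. As an assumption, take n = 25 to 50 of 63 (25/63 = 39.7%; 50/63 = 79.4%).

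- r = 0: no events move.
- r = 1%: 25 × 0.01 = 0.25 to 50 × 0.01 = 0.50 events.
- r = 5%: 25 × 0.05 = 1.25 to 50 × 0.05 = 2.5 events.

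The 5% is the two AV-block discontinuations in the Phase 1 multiple-dose cohorts, 2/40. The 40 is inferred from 35 participants being 88% and 31 being 78%. It is not an estimate for this setting. Protocol 2.2.2.6 does not show that these events followed a first dose, and it ties the second-degree block to titration in the 20 mg cohort. The only single-dose AV block it names was at 40 mg, and the heart-rate fall was dose-related. At 3 mg, r may be close to zero.

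**The case against.** The strongest reply is that the two sections do different jobs. SAP 5.1 decides which records enter the cut, and its sentence may mean only start date rather than end date. SAP 17.1.1 decides the period, by date and time, and says its Induction set is the one used in this analysis. SAP 5.1 also lists entry into the OLE among the ways Induction participation ends, which gives last participation a meaning. The Visit 8 clause shows that a pre-dose boundary was intended on shared days.

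Much of this stands. A reader might infer that SAP 5.1 plainly counts every AE starting on the shared date as Induction. The documents do not support that, because the same section bars OLE data and 17.1.1 points the other way. What remains is a stated rule that gives the wrong period if followed as written, with no time-of-day clause, no mention of the current OLE Visit 1, and no rule for a missing time at the first OLE dose.

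It is also true that first-dose effects by randomized arm are measured on Induction Day 1 by serial ECG, vital signs and Holter. Those data are untouched.

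**Conclusion.** The inconsistency is real and minor. The date-only sentence in SAP 5.1 conflicts with SAP 17.1.1 and with the bar on OLE data in its own section, in a situation that the protocol makes the default. Harm requires that the literal sentence be programmed and that a former-placebo participant has an AE after the open-label dose on the shared date. Its size cannot be determined from the documents and is probably small at 3 mg. Primary and key secondary efficacy, alpha and sample size are unaffected.

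A reader might go further and infer that roughly 40% to 79% of the drug-placebo excess in cardiac events would be hidden. That range only restates the assumed same-day rollover share and presumes the literal reading. It also applies to OLE Day 1 events alone, whereas the Induction table covers 13 weeks, including titration to 30 or 60 mg.

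**What to change.** In SAP 5.1, state that AEs and medications starting on the date of the first LTE or OLE dose enter the Induction Period Analysis only if onset precedes that dose by date and time. In SAP 17.1.1, end Induction at that dose. Name the in-clinic eCRF dosing record as the source of the dose time; Protocol 6.9 already requires it to be recorded. Add a rule for shared-date AEs with no onset time, for example assigning them to the extension period and listing them.

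Repeating the cardiac targeted-event table with those untimed events counted as Induction, and clarifying the Table 3 footnote, are optional. The cost is a few sentences before the interim lock, with no new data or procedures.

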5.2 Final Analysis

After the last participant completes the study, data accumulated over the entire study including LTE/OLE Treatment Periods will be presented in summaries and listings.

6. DETERMINATION OF SAMPLE SIZE

Approximately 189 eligible participants will be randomized in the study. The study is powered to show superiority of VTX002 60 mg to placebo with respect to clinical remission at Week 13.

Based on literature data review, the expected proportion of clinical remission at Induction Week 13 is 28% for VTX002 60 mg and 8% for placebo (Sandborn 2016; Sandborn 2020). Under these assumptions, and with a 1:1 randomization ratio, two-group chi-squared test, and two-sided significance level of 5%, a sample of 57 participants per treatment group will be sufficient to achieve at least 80% power. Adding a 10% inflation for dropouts results in 63 participants per treatment group and 189 participants in total.

All sample size calculations were conducted in SAS 9.4.

7. ANALYSIS ENDPOINTS

7.1 Primary Endpoint

- The proportion of participants with clinical remission at Week 13 using MMS

7.2 Secondary Endpoints

Key Secondary Endpoints

- The proportion of participants with endoscopic improvement at Week 13
- The proportion of participants with symptomatic remission at Week 13
- The proportion of participants with histologic remission at Week 13
- The proportion of participants with endoscopic improvement-histologic remission at Week 13

Other Secondary Endpoints

- The proportion of participants with clinical response using MMS at Week 13
- The proportion of participants with endoscopic remission at Week 13
- The proportion of participants with endoscopic and histologic remission at Week 13
- The proportion of participants with endoscopic and clinical remission at Week 13
- The proportion of participants with endoscopic, histologic, and clinical remission at Week 13

- The proportion of participants with symptomatic remission at Weeks 4, 8, 10
- The proportion of participants with symptomatic response at Weeks 4, 8, 10, 13
- The proportion of participants with clinical remission using total Mayo Clinic score (MCS) at Week 13
- The proportion of participants with clinical response using total MCS at Week 13
- The proportion of participants with histologic improvement at Week 13
- The proportion of participants with histologic-endoscopic mucosal improvement (HEMI) at Week 13
- Proportion of participants with any decrease from baseline in Geboes Index score at Week 13
- The proportion of participants with UC-related hospitalizations
- The proportion of participants requiring UC-related surgeries, including colectomy
- Plasma concentrations of VTX002, assessed from samples collected predose at Weeks 0, 1, 4, 8, and 13 in the Induction Treatment Period, and Weeks 18, 26, 36, and 52 in the LTE Treatment Period; at the 1-Week and 2-Week Follow-Up visits; and at 2, 4, and 6 hours (\pm 15 minutes) postdose at Week 0

7.3 Safety Endpoints

- Incidence and severity of adverse events (AEs)
- Incidence and severity of laboratory abnormalities, and change from baseline in laboratory values (e.g., hematology and serum chemistry)
- Incidence of clinically significant vital sign abnormalities and changes from baseline

7.4 Exploratory Endpoints

The endpoints described here will be analyzed separately, where appropriate, for the Induction Treatment Period, LTE, and OLE. LTE and OLE analyses for the same endpoint may differ not only with respect to the participant set but also with respect to statistical methodology.

- Proportion of participants with histologic remission at Week 13 using RHI
- Proportion of participants with histologic remission at Week 13 using NHI
- Proportion of participants with histologic improvement at Week 13 using RHI
- Proportion of participants with histologic improvement at Week 13 using NHI
- Proportion of participants with clinical remission after 52 weeks of treatment
- Proportion of participants with clinical remission after 13 and 52 weeks of treatment

- Proportion of participants with symptomatic remission at Weeks 18, 26, 36, and 52
- Proportion of participants with endoscopic remission with histologic remission after 52 weeks of treatment
- Proportion of participants with endoscopic improvement-histologic remission after 52 weeks of treatment
- Proportion of participants with endoscopic and clinical remission after 52 weeks of treatment
- Proportion of participants with endoscopic remission, histologic remission, and clinical remission after 52 weeks of treatment
- Proportion of participants with HEMI after 52 weeks of treatment
- Proportion of participants with clinical response after 52 weeks of treatment
- Proportion of participants with symptomatic response at Weeks 18, 26, 36, and 52
- Proportion of participants with symptomatic response at OLE Week 13, and at each additional OLE visit
- Proportion of participants with any decrease from baseline in Geboes Index score at Week 52
- Change from baseline in fecal calprotectin (FCP) at Weeks 1, 4, 8, 13, 26, 36, 52, and at visits during the OLE
- Change from baseline in C-reactive protein (CRP) at Weeks 1, 4, 8, 13, 26, 36, 52, and at visits during the OLE
- Change from baseline in partial Mayo score (PMS) at Weeks 4, 8, 13, 18, 26, 36, 52, and at visits during the OLE
- Change from baseline in total MCS at Week 52
- Change from baseline in Inflammatory Bowel Disease Questionnaire (IBDQ) score at Weeks 13 and 52
- Change and percentage change from baseline in lymphocyte counts at Weeks 1, 4, 8, 13, 26, 36, and 52

7.5 Endpoint Definitions

Clinical remission: SF subscore = 0 or 1, RB subscore = 0, and $ES \leq 1$ (excluding friability)

Clinical response using MMS: $A \geq 2$ -point and $\geq 30\%$ decrease from baseline in MMS, and a ≥ 1 -point decrease from baseline in RB subscore or an absolute RB subscore ≤ 1

Clinical remission using total MCS: Total MCS ≤ 2 points with no individual subscore > 1 point (SF subscore = 0 or 1, RB subscore = 0, $ES \leq 1$ [excluding friability], Physician Global Assessment [PGA] ≤ 1 , and SF + RB + ES + PGA ≤ 2)

Clinical response using total MCS: $A \geq 3$ -point and $\geq 30\%$ decrease from baseline in total MCS, and a ≥ 1 -point decrease from baseline in RB subscore or an absolute $RB \leq 1$.

Endoscopic improvement: $ES \leq 1$ (excluding friability)

Endoscopic remission: $ES = 0$

Histologic improvement

- Primary: Geboes Index score < 3.1
- Sensitivity: Robarts Histopathology Index (RHI) $\geq 50\%$ reduction from baseline or $RHI \leq 3$
- Sensitivity: Nancy Histopathology Index (NHI) ≥ 1 point reduction from baseline

Histologic remission

- Primary: Geboes Index score < 2.0
- Sensitivity: $RHI \leq 3$ with scores of 0 for both Geboes Grade 2B and Grade 3
- Sensitivity: $NHI \leq 1$

Endoscopic improvement-histologic remission: $ES \leq 1$ (excluding friability) and histologic remission measured by a Geboes Index score < 2.0

Endoscopic remission with histologic remission: $ES = 0$ and histologic remission measured by a Geboes Index score < 2.0

Histologic-endoscopic mucosal improvement (HEMI): $ES \leq 1$ (excluding friability) and histologic remission measured by a Geboes Index score < 3.1

Symptomatic remission

- Primary: SF subscore = 0 or 1 and RB subscore = 0
- Sensitivity: SF subscore = 0 (or =1 with a ≥ 1 -point decrease from baseline) and RB subscore = 0

Symptomatic response: Decrease from baseline $\geq 30\%$ of the combined RB and SF subscores

Endoscopic and clinical remission: SF subscore ≤ 1 , RB subscore = 0, and ES subscore = 0

Endoscopic remission with histologic remission and clinical remission: SF subscore ≤ 1 , RB subscore = 0, ES subscore = 0, and histologic remission measured by a Geboes Index score < 2.0

